3.3.3 Exclusion criteria

1. Evidence of current or previous clinically significant diseases or medical conditions other than lupus, or findings of the medical examination (including vital signs and ECG) that, in the opinion of the investigator, would compromise the safety of the patient or the quality of the data. This criterion provides an opportunity for the investigator to exclude patients based on clinical judgment, even if other eligibility criteria are satisfied.
2. Significant central nervous system symptoms related to SLE based on investigators assessment.

3. Clinically important acute or chronic infections including but not limited to HIV, hepatitis B or C.
4. Impaired hepatic function defined as serum AST/ALT, bilirubin or alkaline phosphatase > 2 x ULN.
5. Estimated glomerular filtration rate (eGFR) < 30 ml/min/1.73m² at screening (using CKD-EPI formula).
6. Known hypersensitivity to any constituents of the trial medication; and/or contraindications to MMF or AZA or glucocorticoids.
7. The use of any restricted medications (see [section 4.2.3.1](#)) or any drug considered likely to interfere with the safe conduct of the trial.
8. Unable to comply with the protocol in the investigator's opinion.
9. Chronic alcohol or drug abuse or any condition that, in the investigator's opinion, makes them an unreliable trial patient or unlikely to complete the trial.
10. Women who are pregnant, nursing, or who plan to become pregnant while in the trial.

3.3.4 Withdrawal of patients from therapy or assessments

Patients may potentially be withdrawn from trial treatment or from the trial as a whole ("withdrawal of consent") with very different implications, please see sections [3.3.4.1](#) and [3.3.4.2](#) below.

Every effort should be made to keep patients in the trial if possible, on treatment or at least to collect important trial data. Measures to control the withdrawal rate include careful patient selection, appropriate explanation of the trial requirements as well as the explanation of the safety follow up after a potential withdrawal.

It should be avoided that withdrawn patients would become lost to follow up, therefore safety visits or at least phone calls shall be conducted until 52 weeks after study start (V1 for group 1 and V2 for group 2). See also [6.2.3.3](#).

3.3.4.1 Withdrawal from trial treatment

An individual patient is to be withdrawn from trial treatment if:

- The patient wants to withdraw from trial treatment, without the need to justify the decision.
- The patient needs to take concomitant drugs that interfere with the investigational product or other trial medication (see [section 4.2](#)).
- The patient can no longer be treated with trial medication for other medical reasons (such as surgery, adverse events, other diseases, or pregnancy).
- The patient has repeatedly shown to be non-compliant with important trial procedures and, in the opinion of both, the investigator and sponsor representative, is not willing or able to adhere to the trial requirements in the future.
- The patient develops an anaphylactic reaction (see [section 4.2.2](#)).
- In case of worsening or flare, if deemed appropriate by the investigator, the patient will be discontinued from the trial treatment to receive rescue therapy as per the available guidelines for the treatment of LN.

- The patient experiences an infection with SARS-CoV-2 (as confirmed by local PCR test). The patient may resume trial treatment following recovery from SARS-CoV-2 infection if a negative test for SARS-CoV2 was taken and the patient is expected to derive clinical benefit, as agreed between the investigator and sponsor.

Please note that withdrawal from trial treatment should not necessarily lead to withdrawal from the study. Given the patient's agreement, the patient will undergo the procedures for early treatment discontinuation and follow up as outlined in the [Flow Charts](#) and [section 6.2.3](#).

For all patients, the decision to withdraw from trial treatment (e.g. adverse events) or from the whole trial as well as the reason must be documented in the patient files and recorded in the eCRF. These data will be included in the trial database and reported.

3.3.4.2 Withdrawal of consent for trial participation

Patients may withdraw their consent for trial participation at any time without the need to justify the decision. This will however mean that no further information may be collected for the purpose of the trial and negative implications for the scientific value may be the consequence. Furthermore, it may mean that further patient follow-up on safety cannot occur.

If a patient wants to withdraw consent, the investigator should explain the difference between treatment withdrawal and withdrawal of consent to trial participation and explain the options for continued follow up after withdrawal from trial treatment, please see [section 3.3.4.1](#) above.

3.3.4.3 Discontinuation of the trial by the sponsor

Boehringer Ingelheim reserves the right to discontinue the trial overall or at a particular trial site at any time for the following reasons:

1. Failure to meet expected enrolment goals overall or at a particular trial site.
2. Emergence of any efficacy/safety information invalidating the earlier positive benefit-risk assessment that could significantly affect the continuation of the trial.
3. Violation of GCP, the trial protocol, or the contract impairing the appropriate conduct of the trial.
4. The sponsor decides to discontinue further development of BI 655064.

The investigator / the trial site will be reimbursed for reasonable expenses incurred in case of trial termination (except in case of the third reason).

4. TREATMENTS

4.1 INVESTIGATIONAL TREATMENTS

The trial medication will be provided by Boehringer Ingelheim Pharma GmbH & Co KG, Biberach, Germany.

4.1.1 Identity of the Investigational Medicinal Products

Details of the trial medication are provided below.

Table 4.1.1: 1 Investigational Medicinal Product 1

Substance:	BI 655064
Pharmaceutical formulation:	Solution for injection
Source:	Boehringer Ingelheim Pharma GmbH & Co. KG
Unit strength:	120mg/pre-filled syringe and 180mg/pre-filled syringe
Posology	Group 1 patients: 1 injection per week.
Route of administration:	s.c.

Table 4.1.1: 2 Investigational Medicinal Product 2

Substance:	Placebo
Pharmaceutical formulation:	Solution for injection
Source:	Boehringer-Ingelheim Pharma GmbH & Co. KG
Unit strength:	Placebo to match 120mg BI 655064 Placebo to match 180mg BI 655064
Posology:	Group 1 patients: 1 injection per week.
Route of administration:	s.c.

4.1.2 Selection of doses in the trial

The different doses of BI 655064 used in the induction trial, 1293.10, were selected based on the results of preclinical studies, the 1293.1 Caucasian SRD study, 1293.8 Asian SRD study and 1293.2 MRD study as well as the results from modelling of exposure in chronic treatment of LN. Treatment with BI 655064 has been well tolerated with no dose-dependent safety concerns identified so far (see [section 1.3](#)). Refer to the Investigator's Brochure ([U11-1925](#)) and [section 4.1.3](#) below for further information on dosing in 1293-0013 trial.

4.1.3 Method of assigning patients to treatment groups

Group 1 patients will continue to receive the same treatment allocation as previously assigned in the 1293.10 trial (i.e., either 120mg or 180mg or 240mg or Placebo) at Visit 1.

The assignment will occur in a blinded fashion via Interactive Response Technology (IRT). Details regarding the use of IRT are described in the site IRT user manual available in the ISF.

4.1.4 Drug assignment and administration of doses for each patient

Each pre-filled syringe of trial medication will be labelled with the trial code and a unique medication identification number. At each applicable visit where trial medication is to be prescribed, the trial sites will be required to complete the medication (re)supply module in IRT. The IRT will then adequately assign enough medication kits for the weekly s.c injections administered by the patient at home until the next onsite visit.

BI 655064 / Placebo will be provided in sterile, preservative-free, non-pyrogenic, single-use pre-filled glass syringes for subcutaneous injection. Any unused product or waste material will be disposed of in accordance with local requirements.

The first dose of trial medication will be administered at the trial site for all eligible patients by the investigator (or a suitably qualified designee).

All subsequent doses shall be done by self-injection at the patient's home. For group 1 patients is it acceptable to do the first study drug administration at home, as it is not considered to be a safety or compliance issue because these patients have injected themselves in the previous trial for one year already

After proper training on the administration technique for self-injection and if the investigator determines that it is appropriate with medical follow-up as necessary, the patients will be instructed to self-inject the trial medication at home in between onsite visits on the same day of each week (+/- 1 day). Further information on self-injection technique and instructions for use will be available in the ISF for providing to patients. In case of missed dose, the patient should immediately contact the study investigator for guidance on further dosing.

Table 4.1.4: 1 Dosage and treatment schedule for patients in Groups 1 and 2

Patient Group	Treatment arm & Dose regimen	BI 655064 120mg	BI 655064 180mg	BI 655064 240mg	Placebo
Group 1	Baseline to EOT	120mg q2w	180mg q2w	120mg q1w	Placebo
	Syringes to be administered weekly	1 x 120mg BI 655064 syringe alternating with 1 x Placebo syringe	1 x 180mg BI 655064 syringe alternating with 1 x Placebo syringe	1 x 120mg BI 655064 syringe	1 x Placebo syringe

Dose modification is not permitted during the treatment period. In addition, dilution of the trial medication or the use of other syringes or other needles than those specifically provided by the sponsor is prohibited.

Group 1 patients only: In case a patient cannot be rolled over (only for administrative issues) within the timeframe defined in [section 6.2.1](#), but for ethical reasons the patient shall still be given the chance to continue into 1293-0013, approval must be obtained from CTL/TMM. It will be decided on a case by case basis how to overcome the prolonged treatment interruption between the trials, which may include changing the order in which the initial injections are given to the patient or which may include adding a loading dose at the beginning of the trial.

During the COVID-19 pandemic, physical visits to the sites may need to be restricted to ensure patient safety. Based on a thorough assessment of the benefits and risks, the investigator may still decide to continue the trial treatment and trial medication may be shipped to the patient's home if acceptable according to local law and regulations (for more details see [section 6.2.2](#)).

4.1.5 Blinding and procedures for unblinding

4.1.5.1 Blinding

In this double-blind trial, all patients, investigators and sponsor staff (except those BI members independent of the trial team that will perform the primary analysis) will remain blinded with regard to the randomised treatment assignments.

After the final analysis of the preceding trial 1293.10 it was revealed that the primary endpoint was not reached. An independent DMC reviewed the topline results of 1293.10 and unblinded efficacy and safety results of the ongoing Group 1 in trial 1293-0013 and recommended to continue trial 1293.0013. Taking this recommendation into consideration, a Benefit Risk Committee concluded that the benefit-risk for patients in Group 1 of trial 1293-0013 is unchanged but decided that treatment of patients remaining in the trial should be unblinded.

The unblinding step was taken on 20 Oct 2020 and communicated to the applicable investigators. All other patients who had already completed or early discontinued the trial at that timepoint and were no longer in follow up remain blinded.

For the remaining patients who were not unblinded, a limited number of sponsor personnel will have the potential to be unblinded; however, sponsor personnel involved in the conduct of 1293-0013 (e.g. trial monitor and local monitors) will remain blinded until completion of 1293-0013. These investigators and patients will also remain blinded until completion of the trial.

For Group 1 IRT will be used in 1293.10 for the assignment of patients to treatment groups and the randomisation sequence generated using validated software and verified by an independent BI statistician who is not involved in the planning or performance of the trial. The randomisation code will be kept confidential by Clinical Trial Support up to DBL. For Group 1.

The randomisation codes will be provided to bioanalytics prior to last patient out to allow for the exclusion from the analyses of pharmacokinetic (PK) samples taken from placebo patients. Bioanalytics will not disclose the randomisation code or the results of their measurements until the trial is officially unblinded.

4.1.5.2 Unblinding and breaking the code

Emergency unblinding will be available to the investigator via IRT. It must only be used in an emergency situation when the identity of the trial drug must be known to the investigator in order to provide appropriate medical treatment or otherwise to assure the safety of trial participants. The reason for unblinding must be documented in the source documents and/or on appropriate eCRF page along with the date and the initials of the person who broke the code; and the Sponsor must be informed immediately.

Due to the requirements to report Suspected Unexpected Serious Adverse Reactions (SUSARs), it may be necessary for a representative from BI's Pharmacovigilance group to access the randomisation code for individual patients during trial conduct. The access to the code will only be given to authorised Pharmacovigilance representatives and not be shared further.

4.1.6 Packaging, labelling, and re-supply

BI 655064 and Placebo supplies will be provided by BI or a designated CRO. Each prefilled syringe of trial medication will be packaged in individual carton and labelled in accordance with the principles of Good Manufacturing Practice. Refer to the ISF for details of packaging and description of the label.

Re-supply to the sites will be managed via an IRT system, which will also monitor expiry dates of trial medication supplies available at the sites.

4.1.7 Storage conditions

Each prefilled syringe will be kept in its original packaging until administration in order to protect from light and stored according to the recommended storage conditions on the medication label at 2-8°C (36-46°F). It cannot be frozen. A temperature log must be maintained for documentation.

If the storage conditions are found to be outside the specified range, the local clinical monitor must be contacted immediately. For temperature deviations during shipping to sites and depots, refer to the ISF for instructions.

4.1.8 Drug accountability

The investigator, pharmacist, or investigational drug storage manager will receive the investigational drugs delivered by the sponsor when the following requirements are fulfilled:

- Approval of the clinical trial protocol by the IRB / ethics committee,

- Availability of a signed and dated clinical trial contract between the sponsor and the investigational site,
- Approval/notification of the regulatory authority, e.g. competent authority,
- Availability of the curriculum vitae of the Principal Investigator,
- Availability of a signed and dated clinical trial protocol,
- Availability of the proof of a medical license for the Principal Investigator if applicable,
- Availability of FDA Form 1572 (for USA only).

Investigational drugs are not allowed to be used outside the context of this protocol. They must not be forwarded to other investigators or clinics. Patients should be instructed to return unused investigational drug.

The investigator, pharmacist, or investigational drug storage manager must maintain records of the product's delivery to the trial site, the inventory at the site, the use by each patient, and the return to the sponsor or warehouse / drug distribution centre or alternative disposal of unused products. If applicable, the sponsor or warehouse / drug distribution centre will maintain records of the disposal.

These records will include dates, quantities, batch / serial numbers, expiry ('use-by') dates, and the unique code numbers assigned to the investigational product and trial patients. The investigator / pharmacist / investigational drug storage manager will maintain records document adequately that the patients were provided the doses specified by the protocol and reconcile all investigational products received from the sponsor. At the time of return to the sponsor or appointed CRO, the investigator / pharmacist / investigational drug storage manager must verify that all unused or partially used drug supplies have been returned by the clinical trial patient and that no remaining supplies are in the investigator's possession.

4.2 OTHER TREATMENTS, EMERGENCY PROCEDURES, RESTRICTIONS

4.2.1 Other treatments and emergency procedures

Standard of care (SOC) treatment

All patients will continue to receive SOC treatment for LN of either MMF or AZA in combination with glucocorticoids (if not tapered down to 0mg).

It is acceptable to switch a patient from mycophenolate mofetil to mycophenolate sodium as long as the dose is documented as to mycophenolate mofetil equivalent in the CRF. For simplicity reasons the entire protocol refers to MMF only.

The SOC treatment (MMF and/or AZA) will be procured locally and prescribed at the trial site by the investigator. The sponsor will reimburse the costs for SOC treatment during the trial period in accordance with local regulations.

- MMF and AZA will be considered auxiliary medicinal product (AMP) in this trial. MMF: a stable dose of 1 to 2 g/d. It is recommended not to increase MMF above 2g/d to reduce the risk of MMF related severe side effects. In case of side effects, MMF dose may be reduced to 1g/d; or in case of intolerance, switch to AZA at 2mg/kg/day.

- Patients deviating from the above mentioned dose ranges shall be pre-approved by the CTL/TMM whether they can be enrolled in the trial or not.
- Patients on less than 1g/d MMF before entering the trial may be eligible, if it is documented that the patient did not tolerate higher doses.
- Patients on more than 2g/d MMF before entering the trial may be eligible only if the patient did not suffer from any side effects considered possibly related to MMF in the past.
- AZA: 2mg/kg/day. In case of intolerance or the body weight <50kg, dose may be reduced to 1mg/kg/day or the dosage should be rounded to the nearest 50mg. In regions where only a fixed single dosage is available on the market, the rounding should be done according to the investigators judgment, not exceeding 2mg/kg/day.
- Glucocorticoids: At Visit 1 recommended ≤ 10 mg/d prednisone-equivalent for group 1 patients (depending on actual dose at the end of 1293.10). The tapering of steroids should be performed as follows:
 - Group 1:
 - Patients with a CRR or proteinuria of <0.8g/d at the end of 1293.10 should start steroid tapering immediately at Visit 1. If necessary, patients may remain on a certain level of steroids due to other symptoms of SLE based on investigator's judgement. Although the tapering schedule will allow some flexibility, however steroids should be stopped at 3 months (Week 12) after roll over. If this is not possible due to the patient's medical condition, the patient can stay on the lowest possible dose with the best benefit.
 - Patients with proteinuria of ≥ 0.8 g/d at the end of 1293.10 should taper steroids down to ≤ 7.5 mg/d at week 26 and then to ≤ 5 mg/d at week 52.

In case of worsening or renal flare occurs at any time point, patients will be allowed treatment with higher dose of steroids; alternatively, the investigator may allow patients to receive rescue therapy in according to the available guidelines for LN treatment. For the study analysis, these patients will be considered treatment failures.

However, in any case, deviating from the tapering scheme due to medical reasons will not exclude the patient from the trial.

Adjunctive treatments

All patients should continue taking adjunctive treatments if started before screening such as:

- Hydroxychloroquine at 200 – 400 mg/day or other anti-malarial (such as chloroquine).
- Angiotensin-converting enzyme inhibitor or angiotensin receptor blocker,
- Sstatins.

It is recommended that patients to remain on stable doses for these treatments during the duration of the study.

There are no special emergency procedures to be followed.

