7.5 HANDLING OF MISSING DATA

As an imputation technique to deal with missing data in this study, for the analysis of primary and CRR-related secondary endpoints, non-completers considered failure will be used. Further details on the imputation approaches will be specified in the TSAP.

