3. INTRODUCTION

The purpose of this document is to provide a more technical and detailed elaboration of the principal features of the analysis than was described in the protocol, and to include detailed procedures for executing the statistical analysis of the primary and secondary endpoints and other data.

This TSAP assumes familiarity with the Clinical Trial Protocol (CTP), including Protocol Amendments. In particular, the TSAP is based on the planned analysis specification as written in CTP Section 7 “Statistical Methods and Determination of Sample Size”. Therefore, TSAP readers may consult the CTP for more background information on the study, e.g., on study objectives, study design and population, treatments, definition of measurements and variables, planning of sample size, randomization.

SAS[®] Version 9.4 (or later version) will be used for all analyses.

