5. ENDPOINT

5.1 PRIMARY ENDPOINT

The primary endpoint is the proportion of patients with complete renal response (CRR) and without any renal flares at week 52. CRR is defined as:

UP < 0.5 g/d at week 52

and either

eGFR within normal range at week 52

or

decrease in eGFR < 20% from baseline at week 52 if eGFR is below normal range (i.e., below Lower Limit of Normal, where LLN = 90 ml/min)

For the assessment of proteinuria, 24h urine collection was performed at baseline (which is Week 52 in trial 1293.10) and Week 52 in trial 1293.13. Collection was performed in duplicate (2 times 24h collection). The value of proteinuria is the average of the two values. Blinded review of the volumes of the 24h collections and durations of collection in trial 1293.10 raised concern that some collections may have been incomplete. The rules implemented in 1293.10 that the 24h samples should be ≥ 500 mL/day and at least 19.5 hours (approximately 80% of 24 hours) to be evaluable were applied in 1293.13 also. With respect to UP, any collections < 500 mL/day or < 19.5 hours were not evaluated.

Rules for deriving UP from 24h urine collections to determine CRR

Protein excretion rates were transferred to BI in units of mg/dL. The following steps were performed to convert to g/day for deriving CRR.

Protein excretion rate (mg/dL) x 1/100 = Protein excretion rate (mg/ml)

Protein excretion rate (mg/ml) x 24-hour total volume (ml) = UP (mg)

UP (mg) * 1/1000 = UP (g/day)

An alternative way to derive CRR is based on the ratio of urine protein/urine creatinine (UP/UC) determined from the 24h collections. As the total amount of creatinine excreted daily in the urine is quite stable, UC can be used to stabilize the estimate of proteinuria and is generally accepted as a correction for incomplete collections. When this derivation was applied, collections < 500 mL/day or < 19.5 hours were evaluated.

Both derivations of CRR are included in the CTP section on assessments of renal response. The CTP specifies that the decision which derivation to select as primary endpoint will be based on review of blinded data. However, it was decided to use UP from the 24h collection as the primary derivation for CRR to be consistent with 1293.10. The alternate derivation will be analysed and presented using the same methods/format used for CRR derived from UP.

Proprietary confidential information © 2021 Boehringer Ingelheim International GmbH or one or more of its affiliated companies

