	C4	Medication code broken inappropriately	Medication code broken inappropriately - reason for medication code break <reason> (manual PV)	PPS
D		Concomitant medication		
	D1	Prohibited medication use (as described in CTP, section 4).	
 • Abatacept or Cyclophosphamide during treatment period • Cyclosporine / Tacrolimus / Mizoribine during treatment period (permitted during follow up per investigator's decision) • Belimumab or other "anti- BLYS" or another investigational drug during treatment period • Biologic B-cell depleting therapy (e.g. anti-CD20) during treatment period • IV glucocorticoids during treatment period (Automatic & Manual iPVs)	PPS/ (TBD at MQRM/BRPM)
	D2	Non-permitted oral steroid use (as described in CTP, section 4.2.1)	
 • Patients with a CRR or proteinuria of <0.8g/d at the end of 1293.10 should start steroid tapering immediately at Visit 1. If necessary, patients may remain on a certain level of steroids due to other symptoms of SLE based on investigator's judgement. Although the tapering schedule will allow some flexibility, however steroids should be stopped at 3 months (Week 12) after randomisation. If this this not possible due to the patient's medical condition, the patient can stay on the lowest possible dose with the best benefit. • Patients with proteinuria of ≥0.8g/d at the end of 1293.10 should taper steroids down to ≤7.5mg/d at week 26 and then to ≤5mg/d at week 52. 	PPS/ (TBD at MQRM/BRPM)

[figure not shown]
Proprietary confidential information © 2021 Boehringer Ingelheim International GmbH or one or more of its affiliated companies

Table 6.2: 1 (continued) Handling of iPDs

	D4	Non-permitted AZA dose	AZA is allowed at a stable dose of 2mg/kg/day. (In case of intolerance or the body weight <50kg, dose may be reduced to 1mg/kg/day or the dosage should be rounded to the nearest 50mg. In regions where only a fixed single dosage is available on the market, the rounding should be done according to the investigators judgment, not exceeding 2mg/kg/day.)	PPS/ (TBD at MQRM/ BRPM)
	D5	Non-stable dose of ACE inhibitors or ARBs	ACE inhibitors or ARBs allowed at stable dose.	PPS/ (TBD at MQRM/ BRPM)
G		Trial specific		
	G1	Failure to remove patient from therapy (=study medication)	As described in CTP section 3.3.4.1	PPS/ (TBD at MQRM/ BRPM)
Z		Other		
	Z1	Other iPVs affecting efficacy and possibly safety		PPS/ (TBD at MQRM/ BRPM)

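### A patient given more oral steroid for worsening is a treatment failure under Protocol 4.2.1 but can be scored a responder on the SAP's primary endpoint

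*Protocol*

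**What the plan says.** **Protocol.** Section 4.2.1 covers worsening or renal flare at any time: "patients will be allowed treatment with higher dose of steroids; alternatively, the investigator may allow patients to receive rescue therapy". It then gives the consequence for the analysis: "For the study analysis, these patients will be considered treatment failures". Stopping trial drug is a separate matter and is left to judgement in section 3.3.4.1: "In case of worsening or flare, if deemed appropriate by the investigator, the patient will be discontinued from the trial treatment". Section 4.2.1 also allows steroid for reasons other than the kidney: "patients may remain on a certain level of steroids due to other symptoms of SLE". The only failure rule in the statistical section is in 7.5: "non-completers considered failure will be used".

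**SAP.** Section 3 says that "the TSAP is based on the planned analysis specification as written in CTP Section 7". Section 5.1 builds the primary endpoint from "UP < 0.5 g/d at week 52", an eGFR condition and absence of renal flare. Section 6.6.1 then has two blocks:

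- For patients who stay on drug, it gives only imputation rules for missing urine and creatinine values.
- For patients who stop early, its rule (1) assigns non-response for worsening renal function, flare or rescue. This block is stated not to apply to unblinded placebo patients who stopped injections with the sponsor's approval.

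Deviation D2 in SAP Table 6.2:1 repeats the taper rules of Protocol 4.2.1 but not the failure sentence. The only analysis set D2 names is the per-protocol set (otherwise to be decided), and SAP 6.3 says that set was dropped.

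**The concern.** The two documents appear to score the same patient differently on the primary endpoint. The sentence in Protocol 4.2.1 is an analysis rule, but it sits in the treatment chapter. The SAP is built on Protocol section 7, which does not repeat it, and that is probably how it was lost. The readable text of SAP section 4 does not list the change, and SAP 7.4.2 has no sensitivity analysis that tests it.

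A response reached with added steroid would be credited to the assigned arm. Steroid increases for worsening are foreseeable: all patients are to taper, and Protocol 3.2 says tapering may raise flare risk, perhaps more on placebo. Confirmed CRR, partial renal response (PRR) and the endpoint of proteinuria below 0.8 g/d have the same gap.

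**Working it through.** The plan gives no power calculation (Protocol 7.7) and no figure on this point, so there is nothing to reproduce. The check compares the texts and then gives a scale under stated assumptions.

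**Step 1: trace one patient.** Take a patient whose renal measures worsen without a confirmed flare, who takes more oral steroid, stays on trial drug, and at week 52 has proteinuria below 0.5 g/d with acceptable eGFR.

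| Rule | Applies? | Result |
|---|---|---|
| Protocol 4.2.1 failure sentence | Yes, on its natural reading | Failure |
| SAP 5.1 CRR definition | Met | Responder |
| Flare definition (Protocol 5.1.1) | Not met: needs a laboratory threshold, a repeat test within 2 weeks and no other explanation | No flare |
| SAP 6.6.1, patients who stay on drug | Imputation only | No change |
| SAP 6.6.1 rule (1) | No: patient did not stop early | No change |
| Restricted drugs (Protocol 4.2.3.1) | No: IV glucocorticoids are listed, an oral increase is not | No change |
| SAP deviation D2 | Names only a dropped set | No stated effect on the primary analysis |

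The result is failure under the protocol and responder under the SAP.

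**Step 2: effect of one patient on a response rate.** Shift in percentage points = 100/n. Arm sizes are not given; about 60 patients over four groups would be 60/4 = 15 if equal.

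- n = 10: 100/10 = 10.0
- n = 15: 100/15 = 6.7
- n = 20: 100/20 = 5.0

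**Step 3: effect on the SAP's 0.20 cut-off (7.4.1).** The test is the two-sided Barnard exact test (pooled statistic) with equal arms. Starting responder counts in each arm run from 20% to 80%: 2–8 of 10, 3–12 of 15, 4–16 of 20. Let a be responders on BI 655064 and b responders on placebo. A crossing means that p < 0.20 holds for only one of the two scorings.

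| n per arm | Placebo responder rescored (a ≥ b, b to b−1) | BI 655064 responder rescored (a > b, a to a−1) |
|---|---|---|
| 10 | 5/28 = 17.9% | 3/21 = 14.3% |
| 15 | 7/55 = 12.7% | 6/45 = 13.3% |
| 20 | 10/91 = 11.0% | 8/78 = 10.3% |

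Two examples at 15 per arm:

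- Crosses: 10/15 v 6/15 (p = 0.226) becomes 10/15 v 5/15 (p = 0.099).
- Does not cross: 10/15 v 7/15 (p = 0.328) becomes 10/15 v 6/15 (p = 0.226).

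All pairs are weighted equally, so these fractions are not probabilities.

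**The case against.** The strongest reply has five parts.

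- **The protocol sentence is loose.** The failure sentence could refer to rescue patients only, worsening is not defined, and failure is not tied to a named endpoint. This stands as an ambiguity to settle. On the narrow reading the oral-steroid case falls away, but SAP 6.6.1 still has no rescue rule for patients who stay on drug.
- **Silence is not contradiction.** The SAP assumes familiarity with the protocol and nowhere revokes 4.2.1. But no derivation step applies the sentence, and a programmer following the SAP would score the patient a responder. Where the SAP replaced the non-completer rule of 7.5, it said so and gave a reason.
- **The remaining case is narrow.** Confirmed flares already fail, and restricted drugs, including IV steroids, should lead to stopping trial drug. This is right, and it limits the reach of the point. Neither document shows that an affected patient exists.
- **Other analyses look at steroid use.** SAP 5.2.2 and 7.5.2 plan CRR and confirmed CRR with steroid at or below 5 mg/d, and steroid-free response, from week 26. They are informative, but they miss increases before week 26 and leave the primary endpoint unchanged.
- **A steroid-based failure rule weakens the laboratory-only argument.** The SAP defends the partial unblinding on the ground that the endpoint is laboratory-derived. Steroid decisions are the investigator's, and 29 patients were unblinded. This stands, and it bears on which fix to choose.

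Two limits also apply. Parts of the SAP are redacted, so the absence of a rule can be claimed only for the readable text. The extension to unblinded placebo patients who stopped with approval is an inference: the SAP exempts them from the early-stopper rules without saying which rules do apply.

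**Conclusion.** The concern holds. Followed as written, the SAP can count as a responder a patient whom Protocol 4.2.1 calls a treatment failure, and the readable SAP neither declares nor tests this. The gap is mainly oral steroid increases, in patients who stay on drug, for worsening short of a confirmed flare. It probably extends to unblinded placebo patients who stopped injections with approval.

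The number affected and the direction of any bias are unknown. Under assumed equal arms of 10 to 20, one patient is worth 5 to 10 percentage points. Rescoring one leaves the 0.20 call unchanged in roughly 82% to 90% of the pairs examined. SAP 7.4.1 says the arms are not in fact balanced, p-values are nominal, and Barnard is one of several listed analyses. In an exploratory trial this should be fixed, but it does not by itself undermine the analysis. Confidence is medium because of the ambiguous protocol sentence and the redactions.

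**What to change.** Reconcile the passages before the remaining treatment codes are released, in one of two ways:

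- **(a)** Carry the protocol's failure rule into SAP 5.1 and 6.6.1 for the primary, confirmed CRR, PRR and proteinuria endpoints, whatever the trial-drug status.
- **(b)** State the departure and its reason in SAP section 4, and add a sensitivity analysis of the primary endpoint under the protocol rule.

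Option (b) is the safer route given the 29 unblinded patients, because it keeps the primary endpoint laboratory-based.

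Under either option, state:

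- whether the failure sentence covers steroid increases as well as rescue;
- what counts as worsening;
- how steroid given for non-renal lupus symptoms is classed;
- which rules apply to unblinded placebo patients who stopped with approval.

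Flag cases from the concomitant-therapy records by a rule set in advance, masked to arm where masking is still possible, and report the counts per arm.

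The cost is SAP wording, one flag and, under (b), one extra analysis. Start dates and changes of concomitant therapy are already collected (Protocol 8.3.1). The downsides are that some response rates may fall slightly, the reason for an increase may need judgement, and masking cannot be complete.
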